4.3 Explanation of the Endoprosthesis

Any patient for whom the GORE® EXCLUDER Endoprosthesis® has been withdrawn will be monitored for up to 5 years.

A minimum of one clinical follow-up will be carried out.

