4.4 Premature discontinuation of the research for the patient

The following cases will be considered premature discontinuation of the study:

- Patient withdrawing his non-opposition
- Death
- Failure to Return

A patient who does not show up at the scheduled visit will be considered **temporarily** as having failed to return if the Investigator does not get any information about the patient:

- after having tried to contact him by phone several times (at least two documented phone calls)
- and after having sent him an invitation letter without any reply for 1 month.

All contact attempts will be documented.

If the Investigator obtains news about a temporarily-failed-to-return patient before the end of the study, that patient will no longer be considered failed-to-return; otherwise, he will be permanently categorized as having failed to return at the end of the study.

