4.5 Procedures put in place to avoid failure-to-return

Several measures will be taken to avoid failure-to-return.

The study documents handed over to investigators during study set up highlight the fundamental importance of patient follow-up and data collection during the entire study.

The investigator will seek the means to contact the attending physician or the nearest trusted relation.

In the event of absence from a visit, the center investigator will contact him by phone several times (at least two documented calls) and send him an invitation letter. In the absence of a response, the attending physician will be contacted in a bid to obtain information on the patient's status and on all the elements needed to trace a possible clinical event related to the endoprosthesis (hospitalization, etc.).

In the absence of results from the procedures below, the patient living/deceased status will be documented by investigation in the municipality of birth by the Investigator.

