6.2.2 Criteria Studied

Main analyses:

The criteria studied are as follows:

- Death from all causes
- Aneurysm-related death
- Evolution of the diameter of the aneurysm.
- Types I, II and III endoleaks
- Migration
- Surgical conversion
- Re-intervention related to the initial procedure

Definitions :

- Death related to the aneurysm shall be defined as any death occurring as a result of a ruptured Abdominal Aortic Aneurysm or following any procedure intended to treat Abdominal Aortic Aneurysm.
If the death occurred within 30 days of any procedure intended to treat Abdominal Aortic Aneurysm, then it will be considered as related to the aneurysm unless proven otherwise. Deaths occurring beyond 30 days of any procedure intended to treat Abdominal Aortic Aneurysm and that are related to the procedure should be considered as related to the aneurysm.
- Distal migration is defined by a distal displacement strictly greater than 10mm. Proximal migration is defined either by proximal displacement strictly greater than 10mm, or by proximal displacement which covers one of the renal arteries; the reference examination being the first postoperative CT performed.

- An increase in the diameter of the aneurysm is defined by an increase strictly greater than 5 mm of maximum diameter of the highest measurable diameter of the aneurysm; the reference diameter being the diameter of the first post-operative check-up.

Each of the rates that match the Study criteria will be analyzed by calculating frequency distributions and bilateral confidence intervals of 95% (IC95) associated.

Event rates over time are described by survival curve according to the Kaplan-Meier method and the related Kaplan-Meier estimators will be calculated.

Additional Analyses:

All the analyzes may be stratified by center if recruitment in each center participating in the study is sufficient for such analyzes to be of interest. However, it must be emphasized that this Protocol in no way aims to compare the centers.

For exploratory purposes, the study criteria will also be analyzed depending on patient baseline characteristics:

- Age (in categories)
- Gender
- Diameter of Abdominal Aortic Aneurysm
- Patient status (normal or high surgical risk according to the Afssaps criteria, Appendices 3 and 4)

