6.4 Method of management of missing, unused or invalid data

Missing data will be listed and presented in a tabulated form.

Patients will be considered as censored at the date of the last observation.

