### 1.1. Study Objective

The objective of this study is to assess the usefulness of the technique by documenting overall mortality, complications (endoleak, migration), the rate of surgical conversion, the evolution and rupture of the aneurysm, in the long term, that is, 5 years, on a cohort of patients representative of the population treated in real life conditions.

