### 2.4.3.2. Secondary Analyses

The surgical conversion rate during procedure and the corresponding 95% confidence interval will be provided.

The following parameters will be presented using the Kaplan-Meier survival curves:

- Mortality related to the aneurysm
- Aneurysm diameter evolution
- Endoleak complication, for each type (I, II and III)
- Device migration overall and by type (distal, proximal)
- Re-intervention

For the parameters “Aneurysm diameter evolution”, “Endoleak complication” and “Device migration”, the date to be used for the survival analysis is the date of the first visit where the parameter is reported. Only events occurring up to 5 years (1826 days) of follow-up will be analyzed for these survival curves.

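### Kaplan-Meier is the only time-to-event method named for the secondary endpoints; if deaths without the event are censored, as the protocol's rules imply, the curves overstate the 5-year risk

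*SAP*

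**What the plan says.** SAP 2.4.3.2 introduces the secondary endpoints with "The following parameters will be presented using the Kaplan-Meier survival curves". The list covers aneurysm-related mortality, diameter evolution, endoleak by type, migration overall and by direction, and re-intervention. Events count up to day 1826. SAP 5.1.2.2 gives all ten resulting tables (35 to 44) the same survival layout, Type 10. Protocol 6.2.2 agrees: "Event rates over time are described by survival curve according to the Kaplan-Meier method". It also plans crude rates, each of which "will be analyzed by calculating frequency distributions and bilateral confidence intervals of 95" per cent.

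No readable section says what happens in these curves to a patient who dies without the event. Two general rules bear on it. Protocol 4.4 says "The following cases will be considered premature discontinuation of the study" and lists death beside withdrawal and failure to return. Protocol 6.4 says "Patients will be considered as censored at the date of the last observation". Neither document's readable text mentions competing risks or cumulative incidence.

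**The concern.** A patient who has died can no longer have an endoleak, a migration or a re-intervention. Censoring that patient at the last observation treats the death like a loss to follow-up, as if the event could still occur later at the same rate as in the survivors. 1-KM then estimates the risk in a population in which nobody dies of anything else. It can never lie below the Aalen-Johansen estimate, and it lies above it as soon as one event follows a competing death.

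Death is a real competing event here. The primary analysis is 5-year mortality, the SAP splits age at 80 years, and high surgical risk is a recorded category. The objective is to document these complications "on a cohort of patients representative of the population treated in real life conditions", and the results go each year to the authority that decides on reimbursement. The size of the error depends on mortality and on when events occur, so it differs between endpoints. It runs against the sponsor's own device.

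**Working it through.** **Inputs.** From the documents: n = 180 (SAP 1.3.1), horizon 5 years (1826 days), scans at about 1, 6 and 12 months and then yearly (Protocol 3.2), two-sided 95% intervals. Mortality, event rates, event timing and loss are not given, so everything below on those is assumed and shown as a range. The plan states no figure to reproduce.

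**Step 1: constant hazards.** Let R be the 1-KM reading and D the 5-year competing mortality. Then l = -ln(1-R)/5, m = -ln(1-D)/5, and the actual risk is l/(l+m) × (1 - exp(-5(l+m))).

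Example, R = 20%, D = 25%: l = 0.04463, m = 0.05754, l/(l+m) = 0.4368, and 1 - exp(-5(l+m)) = 1 - 0.80 × 0.75 = 0.40. The actual risk is 0.4368 × 0.40 = 17.5%, so the curve reads 2.5 points too high.

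| Competing mortality | Actual risk when 1-KM = 20% | Excess (points) | Actual risk when 1-KM = 3% | Excess (points) |
|---|---|---|---|---|
| 10% | 19.0% | 1.0 | 2.85% | 0.15 |
| 15% | 18.5% | 1.5 | 2.77% | 0.23 |
| 25% | 17.5% | 2.5 | 2.61% | 0.39 |
| 40% | 15.8% | 4.2 | 2.35% | 0.65 |

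**Step 2: timing.** For a cumulative event hazard L(t), the actual risk is the integral of exp(-L(t) - m t) dL(t). At a 20% reading and 25 / 40% mortality:
- 70% of the hazard in month 1: actual 19.2 / 18.7%, excess 0.8 / 1.3 points.
- Half of the hazard in month 1: 18.7 / 17.9%, excess 1.3 / 2.1 points.
- Hazard rising linearly: 16.6 / 14.5%, excess 3.4 / 5.5 points.

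**Step 3: precision.** 1.96 × √(p(1-p)/180) gives 5.8 points at p = 20% and 2.5 points at p = 3%.

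**Step 4: endpoints seen only on scans.** Simulated patients had exponential event, death and imaging-stop times, were scanned on the protocol schedule, and had all deaths known. Results are for 10 / 20 / 30% stopping imaging.

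| | 25% mortality (actual 17.5%) | 40% mortality (actual 15.8%) |
|---|---|---|
| 1-KM, deaths censored at last imaging | 20.0 / 20.0 / 20.0% | about 20.0% throughout |
| Crude share | 16.1 / 15.1 / 14.1% | 14.4 / 13.5 / 12.6% |
| Aalen-Johansen, all known deaths competing | 16.9 / 16.6 / 16.4% | 14.9 / 14.5 / 14.2% |

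Aalen-Johansen errs low by 0.6 / 0.8 / 1.1 points and 0.9 / 1.3 / 1.6 points. Events arising between the last scan and death are never seen, and missed imaging hides others.

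**Step 5: which deaths to count.** With 10% stopping imaging and a further 10 / 20 / 30% of scans missed at random, counting all known deaths as competing stays at 16.7 to 16.9% (25% mortality) and about 14.5 to 14.9% (40%). Censoring a death after any single missed scan gives 17.9 / 18.6 / 19.3% and about 16.3 / 17.3 / 18.5%, which brings much of the upward bias back. If the death hazard triples once imaging stops (30% stopping, baseline mortality 25%), the actual risk is 17.1% and counting all deaths gives 15.6%. That is a reason for a sensitivity analysis on deaths after imaging has stopped.

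**The case against.** **The rule may sit in text that cannot be read.** SAP 2.1.3 to 2.3, which include missing data, inferential analysis and analysis sets, are absent from the available text. The end of 2.1.2 may be absent too, and the block after 2.4.3.2 is blacked out. Protocol 4.4 and 6.4 are general rules on discontinuation and missing data, not a rule for deaths in these curves. This stands: a reader might infer that the plan definitely censors deaths, and the documents support only that the readable rules imply it.

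**The error may be lost in sampling error.** For a 3% event it is: at most 0.65 points against a half-width of 2.5. For a 20% event it is also smaller than the half-width, but it always points upward, the interval does not reflect it, and a larger cohort would not reduce it. No test or threshold is visible, so no decision rule is affected.

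**Crude rates are also planned.** True, and they lack the upward bias. They count patients lost to follow-up as event-free, so they err low (Step 4) and do not replace a correct time curve.

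**The table layout may count deaths as events.** The Type 10 summary table labels its time variable as progression-free survival. A reader might infer curves of event or death, which at a 20% reading would show 1 - 0.80 × (1 - D), or 28 to 52% for D = 10 to 40%. The documents do not support this: the label is undefined, the same layout serves all-cause mortality in Table 33, and it looks like a template remnant.

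**Conclusion.** The point holds conditionally, with medium confidence. Kaplan-Meier is the only time-to-event method named in the readable text for Tables 35 to 44. If deaths without the event are censored, as Protocol 4.4 and 6.4 together imply, 1-KM overstates the actual 5-year risk.

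On the assumed mortality range, the excess at a 20% reading is about 1 to 4 points under constant hazards and about 1 point if most of the hazard comes in the first month. It is larger only if events come late. For a 3% event it is under 0.7 points. A reader might take the upper end, 2.5 to 4.2 points, as the general size, but that needs 25 to 40% mortality, a common endpoint and constant hazards, none of which the documents give.

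The primary analysis in Table 33 is unaffected, because all-cause death has no competing event. The change is worth making for the accuracy of the reported complication rates; it does not put the study's main result in doubt.

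**What to change.** Confirm or state in the SAP how deaths without the event are handled in Tables 35 to 44. Then:

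- **Estimator.** Report the Aalen-Johansen cumulative incidence with 95% CI at fixed times up to 5 years. The competing event is death from any cause, except in Table 35, where it is death not related to the aneurysm.
- **Table 35.** Keep the protocol's 30-day attribution rule. Add a sensitivity analysis counting deaths of unknown cause first as related, then as unrelated. It is needed because, for patients who cannot otherwise be traced, Protocol 4.5 promises only that "the patient living/deceased status will be documented by investigation in the municipality of birth by the Investigator". That does not assure a cause of death.
- **Imaging endpoints, Tables 36 to 43.** Count all known deaths as competing in the main analysis. As a sensitivity analysis, where imaging had stopped (the last scan due before death was not attended), censor at the last imaging exam. Do not let one missed scan turn a death into censoring.
- **Keep** Kaplan-Meier for Table 33 and as a labelled supplement elsewhere. Keep the crude rates, with the number lost to follow-up beside them.
- **Correct** the progression-free survival label in the Type 10 layout.

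The cost is SAP wording, reprogramming of ten tables and the sensitivity runs. There are two downsides. The main figures become less directly comparable with Kaplan-Meier figures from other cohorts, which the supplementary curves mitigate. The imaging estimates will err low, by about 0.6 to 1.6 points in the illustrations with 10 to 30% stopping imaging or missing scans.

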3.3 Evaluation Criteria

These criteria are measured postoperatively or within one month after surgery, at 6 months, 12 months and then annually for 5 years, with an annual report issued to be submitted to the French National Authority for Health:

- Overall mortality rate,
- Mortality rate related to the aneurysm,
- Evolution of the diameter of the aneurysm
- Rate of Endoleaks for Type I, II and III
- Migration rate,
- Rate of surgical conversion,
- Rate of endovascular or surgical re-intervention.

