#### 1.3.2. Patient's Follow-up

8 visits are scheduled:

- Visit 1 : Baseline
- Visit 2 : Procedure
- Visit 3 : Discharge
- Visit 4 : Post operatory (or in the month following the surgery)
- Visit 5 : 6 months Follow-up
- Visit 6 : 1 year Follow-up
- Visit 7 : 2 years Follow-up
- Visit 8 : 3 years Follow-up
- Visit 9 : 4 years Follow-up
- Visit 10 : 5 years Follow-up

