## 2.4.3. Endpoints Analyses

The endpoint analyses will be performed on the ITT population.

Primary analysis consists to study the 5-year mortality of patients who received the endoprosthesis. Secondary analyses consist to study the other safety parameters on patients who received the endoprosthesis.

The dates to be used for the “aneurysm diameter evolution” survival analysis will be the date of the imaging exam on which it has been reported. If it is missing, the corresponding “clinical exam” date will be used instead.

The same will be done for the “endoleak complication” and “device migration” survival analyses.

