##### *5.1.1.2. Procedure*

Table 20 : Implantation main indication (Type 3)

Table 21 : Duration of procedure (minutes) (Type 1)

Table 22 : GORE® EXCLUDER® AAA Endoprosthesis bifurcated (Type 3)

Table 23 : Access type (Type 3)

Table 24 : Type of anesthesia used (Type 3)

Table 25 : Volume of contrast medium (ml) (Type 1)

Table 26 : Time under fluoroscopy (minutes) (Type 1)

Table 27 : Procedure outcome and failure details (Type 3)

Table 28 : Related surgical/endovascular procedures (Type 3)

Table 29 : Surgical complications (Type 3)

Table 30 : Abnormalities observed (Type 5)

Table 31 : Endoleak (Type 5)

Table 32 : Stay in Intensive Care Unit (hours) (Type 1)

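### The SAP's endoleak curves measure time to first report with no stated start of risk, so they do not show how many patients have a leak at each control up to 5 years

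*SAP*

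**What the plan says.** SAP 2.4.3.2 lists endoleak, by type, among the outcomes shown as Kaplan-Meier curves. For diameter evolution, endoleak and migration it states that "the date to be used for the survival analysis is the date of the first visit where the parameter is reported", and then: "Only events occurring up to 5 years (1826 days) of follow-up will be analyzed for these survival curves". The outputs are Table 37 (overall) and Tables 38 to 40 (types I, II and III), all in the survival-curve layout.

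SAP 2.4.3 gives another dating rule. Diameter evolution is dated by the imaging exam on which it was reported, or by the clinical exam if that date is missing, and "The same will be done for the “endoleak complication” and “device migration” survival analyses".

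The numbered visits in SAP 1.3.2 include "Visit 2 : Procedure". Endoleak is recorded at that visit, because Table 31, listed under Procedure, reports it.

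Protocol 3.3 sets the measurement times: "These criteria are measured postoperatively or within one month after surgery, at 6 months, 12 months and then annually for 5 years". Protocol 6.2.2 asks for more than curves: "Each of the rates that match the Study criteria will be analyzed by calculating frequency distributions and bilateral confidence intervals of 95" per cent, with Kaplan-Meier estimation in addition.

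**The concern.** Unlike death, an endoleak can appear, resolve and recur. A first-report curve records only that a leak was once seen. The readable SAP has no rule for resolution, persistence, recurrence or return to the risk set.

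The protocol itself treats a leak as something to look at again: its visit schedule adds an intermediate examination after one is found. The readable analysis text makes no use of that examination to classify the leak as persistent or resolved.

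The study's objective is the long-term usefulness of the technique at 5 years, and the results go to a body that may recommend that reimbursement be maintained or suppressed. That reader will want to know how many patients have a leak at 1, 3 or 5 years, and of which type. The planned curves do not answer this.

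The undefined start of risk adds a second uncertainty. Two programmers following the SAP could produce different curves, one including leaks recorded at the procedure and one not.

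**Working it through.** **1. What the event rule does.** Take a patient with a type II leak at the D1 to D30 control, none at 6 months, and a new type II leak at year 4. Under SAP 2.4.3.2 this is one event, at the first control. The resolution has no effect and the year-4 leak does not appear in Table 39. In Table 37 (overall), no later leak of any type can appear for this patient. A later leak of a different type would still count in its own table.

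**2. What the output shows.** The survival-curve layout in SAP 4.3.3 gives numbers with and without an event, one survival rate and time percentiles. It has no line for status at a visit. In the readable part of 2.4.3.2, a rate with a 95% confidence interval is specified only for surgical conversion during the procedure.

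**3. Start of risk.**
- Pointing towards inclusion of the procedure: it is Visit 2, endoleak is recorded there, and the duration rule in SAP 2.1.2 (difference in dates plus 1) gives a procedure-day leak a valid time of 0 + 1 = 1 day.
- Pointing towards exclusion: Protocol 3.3 starts measurement post-operatively, the imaging chart in SAP 1.3.4 starts at the D1 to D30 control, SAP 2.4.3 dates leaks by imaging exam, and Table 31 reports procedural leaks apart from the endpoint tables.
- Diameter increase and migration share the dating sentence but not this problem. The protocol ties each to a first post-operative reference examination. It sets no such reference for endoleak.

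**4. Illustrative size.** The documents state no endoleak rate, so there is no planned figure to reproduce and every input here is an assumption:
- e = share of patients with an early leak: 10%, 20% or 30%
- r = share of early leaks that resolve: 50%
- L = risk of a later new leak to 5 years: 15%, also applied to patients whose early leak resolved

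First-report incidence is A = e + (1 − e)L. With resolved early leaks not counted and those patients kept at risk, it is B = e(1 − r) + [1 − e(1 − r)]L. The gap is A − B = e·r·(1 − L).

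| e | A | B | Gap (points) |
|---|---|---|---|
| 10% | 0.10 + 0.90 × 0.15 = 23.5% | 0.05 + 0.95 × 0.15 = 19.3% | 4.25 |
| 20% | 0.20 + 0.80 × 0.15 = 32.0% | 0.10 + 0.90 × 0.15 = 23.5% | 8.5 |
| 30% | 0.30 + 0.70 × 0.15 = 40.5% | 0.15 + 0.85 × 0.15 = 27.8% | 12.75 |

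With L = 10%, e from 5% to 30% and r from 25% to 75%, the gap runs from 1.1 to 20.2 points. As a check on the formulas, a simulated Kaplan-Meier analysis (200,000 patients, 30% censored by death, e = 20%, r = 50%, L = 10%) gave 28.0% and 18.9%, against 28.0% and 19.0% in closed form.

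**5. Scale.** For 180 patients without censoring, the 95% half-width is 1.96 × √[p(1 − p)/180]. This is 4.4 points at 10%, 5.8 at 20% and 6.7 at 30%. In the table above, the gap is below sampling error at e = 10% and above it at e = 20% and 30%.

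**The case against.** Time to first reported endoleak is a legitimate quantity, and Protocol 6.2.2 asks for Kaplan-Meier curves, so the SAP delivers something the protocol wants. This stands: the curves should be kept, under an accurate label.

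A reader might go further and infer that leaks corrected during the procedure are counted as events. The documents do not establish this. No passage sends procedural findings to Tables 37 to 40, and the passages listed under exclusion above point the other way. SAP 2.1.1 also takes the last available observation for a visit, which, applied to Visit 2, would favour status at the end of the procedure. What remains is that the readable text never states the exclusion.

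A reader might also describe these events as permanent failures at 5 years, or say that every late leak after an early one is lost. The SAP makes no claim of failure, and the separate curves by type lose only recurrence of the same type.

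The strongest objection concerns the missing table. The block after SAP 2.4.3.2 and the text after Table 44 are redacted, and SAP 2.1.3 to 2.3 is not visible. Two table layouts (Types 2 and 9) are defined but used by no visible table, so further tables probably exist and endoleak by visit could be among them. The absence is therefore claimed for the readable text only. The event rule itself is readable and does not depend on what is redacted.

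**Conclusion.** The point holds as a mismatch between the planned curve and the long-term question, together with an unstated start of risk. The first-report rule is explicit. Its consequences for resolved leaks and for same-type recurrence follow directly from it.

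Under the stated assumptions it adds about 4 to 13 points to the 5-year figure, which can match or exceed sampling error with 180 patients. That rests on assumed values of e, r and L, and on equal later risk after a resolved leak. The comparison should be made with the figure that still includes persistent early leaks (19.3% to 27.8%). Setting the first-report figure against the 15% later-leak risk alone would exaggerate the effect.

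Whether procedural leaks enter the curves cannot be decided from the text. It is an ambiguity to close, not a demonstrated error.

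**What to change.** In SAP 2.4.3.2:

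1. State that endoleak events for Tables 37 to 40 count from the first post-operative control imaging onward. Procedural findings stay in Table 31, and any imaging at discharge (Visit 3) is assigned explicitly to one side or the other.
2. Reconcile the imaging-date rule in 2.4.3 with the visit-date rule in 2.4.3.2, so that one rule dates each event.
3. Label the curves as first reported endoleak.
4. Unless the redacted text already provides it, add a table of endoleak by type at each scheduled control: patients with the leak over patients imaged, with a 95% confidence interval, split into new, persistent since the previous examination, and resolved.

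The cost is some SAP wording and one table from examinations already scheduled, with no new visits. A small downside is that procedural leaks are reported apart from the curve. Item 1 does not remove leaks that resolve after the first control, so item 4 is needed as well.

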3.2 Conduct of the Study

The Study is conducted according to the usual management schedule for these patients.

After inclusion of the patient, there will be postoperative follow-up or in the months following the procedure and at 6 months, 12 months and annually, for 5 years.

The clinical and radiological follow-up will be performed according to the follow-up protocol recommended by HAS and by Learned Societies (Société de Chirurgie Vasculaire [Society for Vascular Surgery] – Société Française de Radiologie [French Society of Radiology])¹.

	Post-operative follow-up (D1 to D30)	Follow-up at 6 months.	Follow-up at 1, 2, 3, 4 and 5 years	Follow-up intermediate ***
Clinical examination	X	X	X	X
Radiography of the abdomen without preparation in 3 effects (front, profile and ¾)	X ¹	X*	X*	X*
CT with contrast medium	X	X	X	X
MRI	X*	X*	X*	X*
Vascular Doppler	X**	X**	X**	X**

* if CT with contrast medium cannot be performed

** if MRI cannot be performed

*** interim follow-up carried out only in case of leakage, deterioration of the endoprosthesis or scalability of the aneurysm on the previous control examination. Follow-up to be carried out 3 months after the control where the anomaly was observed.

¹ Radiography in postoperative follow-up will not be necessary in case of 3D reconstruction performed during the CT.

An annual report will be forwarded to CNEDiMTS.

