#### 2.1.2. Derived Criteria Calculation

- Age classes will be the following:
  - Age < 80 years
  - Age ≥ 80 years
- Body Mass Index will be calculated as :  

$$\text{BMI} = \text{weight (kg)} / (\text{height (m)})^2$$
- Duration between two dates i and j will be calculated as:  

$$\text{Duration } i, j = \text{Date } j - \text{Date } i + 1$$
- If no clinical exam is done at a particular visit, the visit date will be the last imaging exam date reported for this visit.
- Total study duration will be calculated as:  

$$\text{Total study duration} = \text{study exit date} - \text{procedure date} + 1$$
 If the procedure date is not available, the baseline will be used instead.

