### Summary table

	Mod 1 (n=X)	...	Mod n* (n=X)
Nb of patients	X	...	X
Nb of patients with an event	X (XX.XX%)	...	X (XX.XX%)
Nb of patients without an event	X (XX.XX%)	...	X (XX.XX%)
Survival rate	XX %	...	XX %
Progression-Free survival (days)		...	
Median	XX	...	XX
(95% CI)	(XX, XX)	...	(XX, XX)
25th-75th percentile	XX.X – XX.x	...	XX.X – XX.x
Range	X - X	...	X - X

\* If any

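### In the interim annual reports, the Kaplan-Meier curves for endoleak, migration and diameter increase can drop falsely at their end, because findings are dated, and clear patients are probably censored, at the exam itself

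*SAP*

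**What the plan says.** **Dating of findings.** SAP 2.4.3 says that the date for the diameter-evolution "survival analysis will be the date of the imaging exam on which it has been reported", with the clinical exam date as fallback, and applies the same rule to endoleak and migration. SAP 2.4.3.2 words it as "the date to be used for the survival analysis is the date of the first visit where the parameter is reported". Either way, the event date is the date of detection.

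**Censoring.** Protocol 6.4: "Patients will be considered as censored at the date of the last observation". It does not say whether an observation means an exam, an imaging exam or any contact. SAP 2.1.3 (missing data) is listed in the contents, but its body is not in the text supplied.

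**Estimator.** Protocol 6.2.2: "Event rates over time are described by survival curve according to the Kaplan-Meier method and the related Kaplan-Meier estimators will be calculated". The same section also plans simple frequencies with 95% confidence intervals for each criterion. The text supplied describes no by-control or interval-censored estimate.

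**Time limit.** SAP 2.4.3.2: "Only events occurring up to 5 years (1826 days) of follow-up will be analyzed for these survival curves". SAP 2.1.2 computes a duration as the difference between two dates plus one day.

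**Reporting.** Protocol 3.2: "An annual report will be forwarded to CNEDiMTS". Tables 36 to 43 use the Type 10 layout in SAP 4.3.3, whose summary table has a row "Survival rate" with no time point.

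**The concern.** These three criteria can be seen only when a patient is examined. Each control gives one of two answers, finding or clear. If both answers are entered on the exam date, Kaplan-Meier treats the order of appointments within one control as if it were information on time to event. A patient seen clear on a Monday is out of the risk set when another patient's finding is counted on the Friday, although both had the same control and the same chance of a finding. Each later finding is divided by a smaller number.

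This does no harm at a control that is followed by another, because clear patients stay at risk. It matters at the last control reached, where clear patients are censored. In an interim report that is the same control, or one of two neighbouring controls, for almost everyone, so the distortion sits at the end of the curve.

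The reports go to the authority that decides whether reimbursement is maintained (Protocol 1.1.3). An inflated rate of endoleak or migration there would count against the device.

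**Working it through.** The documents give no expected rate for these criteria, so there is no planned figure to reproduce.

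**Step 1: one control.** Suppose ten patients attend their last control and one has a finding. The correct step is 1/10 = 10%. With exam-date timing the step is 1/r, where r is the number not yet seen, including that patient. If the finding is equally likely at each place in the order, the mean step is (1 + 1/2 + ... + 1/10)/10 = 2.93/10 = 29%. If that patient is seen last, the curve falls to zero.

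In general, for a proportion p with a finding among n patients, the expected cumulative hazard added across the last control is p × H(n), where H(n) = 1 + 1/2 + ... + 1/n. For n = 180, H(n) = 5.77. Read when half the patients have been seen, it is only about p × ln 2 = 0.69p. The answer depends on where the curve is read.

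**Step 2: size over several controls.** From the documents: n = 180, and controls post-operatively, at 6 months and at 1, 2, 3, 4 and 5 years. Assumed: a new finding in 5% post-operatively and 2% at each later control; exam dates with SD 21 days around the nominal date (8 days post-operatively); censoring at the last exam. The true cumulative rate is 1 − 0.95 × 0.98^m after m later controls, for example 1 − 0.95 × 0.98² = 8.8% at year 1. Simulation gives:

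| Report | True | End of curve, mean | End of curve, median | At nominal anniversary, mean |
|---|---|---|---|---|
| Year 1 | 8.8% | 16.8% | 12.4% | 8.2% |
| Year 2 | 10.6% | 18.2% | 14.0% | 10.0% |
| Year 3 | 12.4% | 19.7% | 16.0% | 11.9% |
| Year 4 | 14.1% | 21.1% | 17.8% | 13.6% |

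The mean ratio runs from 16.8/8.8 = 1.9 to 21.1/14.1 = 1.5. The median ratio runs from 12.4/8.8 = 1.4 to 17.8/14.1 = 1.3; repeat runs reach 12.8/8.8 = 1.5. The mean is higher because a few runs have a finding when hardly anyone remains at risk.

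**Step 3: sensitivity.**
- Spread of dates: an SD of 5 days gives much the same year-1 mean (about 16 to 18%), so punctual visits do not help.
- Rate: with 0% post-operatively and 1% per control (migration-like), year 1 is 2.0% true against a mean of 6.6% and a median of 3.4%.
- Censoring later than the exam, year 2 (true 10.6%): a random extra 0 to 30 days gives 12.6%; 0 to 90 days removes nearly all of the inflation. With 12-month entry and a data cut at 26 months, censoring at the cut-off gives 10.7%.
- Estimation by scheduled control recovers the true value within 0.2 to 0.3 points.

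**Step 4: the 5-year report.** The true value is 1 − 0.95 × 0.98⁶ = 15.8%. With events limited to day 1826, the mean estimate is 18.4% if 5-year controls run 30 days early, 15.3% if on time and 14.3% if 30 days late. The underestimate arises because findings after day 1826 are not counted. Five calendar years are at least 5 × 365 + 1 = 1826 days, so under the plus-one duration formula an exam on the exact fifth anniversary falls on day 1827 or later, outside the limit.

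**The case against.** The strongest reply is that the plan does not fix the two conditions on which the effect depends.

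- **Censoring date.** A reader might infer that the documents censor at the last exam. They say only last observation, Protocol 4.5 allows status to be obtained by telephone and from other sources, and SAP 2.1.3 cannot be seen. This stands: censoring at a later contact or at a data cut-off shrinks or removes the inflation. However, the contacts in Protocol 4.4 and 4.5 concern patients who miss a visit. For a patient who attends, the control is normally the latest observation.
- **Reading point.** The Type 10 layout is generic and does not say that the survival rate is the end-of-curve value. Protocol 3.3 lists fixed assessment times, and at the nominal anniversary there is no inflation. This also stands, but nothing visible instructs that reading, and an undated rate invites the end-of-curve value.
- **All reports, doubled.** A reader might infer that every annual report is affected and that rates are roughly doubled. The 5-year report is largely protected by the 1826-day limit, and its error is more often a slight underestimate. Near-doubling describes the mean at year 1, not the typical report.
- **Other estimates.** The frequencies in Protocol 6.2.2 do not carry this error, so the authority would not see only the inflated figure. They do not correct Tables 36 to 43.

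**Conclusion.** The concern holds for the interim annual reports (years 1 to 4), for endoleak, migration and diameter increase, if event-free patients are censored at their last control and the rate is read at the end of the curve. Under the assumed rates the typical inflation is 1.3 to 1.5 times, with a mean of 1.5 to 1.9 times. The rates and the spread of dates are assumptions; the direction and mechanism are not sensitive to the spread. The study's main result at 5 years is little affected unless the 5-year controls run early. The documents do not support a claim that all reports are wrong or that rates generally double. What they do support is that, as written, the interim estimate depends on appointment dates and on an undefined censoring date, and neither says anything about the device.

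**What to change.** In SAP 2.4.3.2, for Tables 36 to 43:

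1. Estimate by scheduled control: a life table in which each patient's earliest positive exam takes the nominal time of its control, with events ranked before censorings on ties. Alternatively, use an interval-censored estimator (last clear exam, first positive exam; Turnbull, available in SAS as PROC ICLIFETEST).
2. State that, for these criteria, event-free patients are censored at their last control with a usable exam. Adopt this together with item 1; on its own, with exam dates kept, it would fix the plan on the reading that produces the error.
3. Replace the undated survival rate by estimates at the control times the cohort has reached, each with the number examined. Do not report the end of the curve.
4. Do not move a finding at an intermediate exam to a later control that clear patients have not reached; in an interim report that would leave mostly positives in the risk set there. Use the interval-censored estimator for such findings, or count them at the next control only for patients whose next control is due by the data cut.
5. State how 5-year exams after day 1826 are counted.
6. Keep exact dates for death and re-intervention.

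The cost is a few lines of SAP text and a small programming change, with no new data. The downside is that the curves step at scheduled controls instead of at exam dates.
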